### **Design of the study:**

#### Prospective enrollment:

This study was a double-blinded randomized controlled trial analyzing 40 patients undergoing major lower extremity amputation by the vascular surgery service at UCSF Fresno at Community Regional Medical Center, Clovis Community Medical Center, and Fresno Heart and Surgical Hospital. All included patients were evaluated by the vascular surgery service and had lower extremity amputation deemed necessary based on ischemic disease, infectious disease, and/or disfigurement. Patients were excluded if they were less than 18 years of age, pregnant, undergoing emergency amputations, staged amputations, or amputations by non-vascular surgeons, have known allergies to bupivacaine, are unable to communicate symptoms of pain, or refuse to participate in the study. Eligible patients were identified by the vascular surgery service in their private office or following a consultation by the vascular surgery service in the hospital. Upon identification, eligible patients or their surrogate decision maker were approached for consent by a member of the study team.

To randomize patients, consent forms were pre-labeled with a random subject identification number. This number served as the participants' study ID for all data collection in order to maintain privacy and confidentiality. Additionally, this number was linked to a sealed envelope containing the random treatment group. The study coordinator created the labels and assembled the envelopes to ensure all investigators remained blind to the treatment groups. This sealed envelope was given to the anesthesia providers, by the vascular surgery service, for the amputation. The anesthesia team then administered the assigned treatment prior to induction of general

anesthesia. Half of the patients were randomized into the treatment group, and half of the patients were randomized into the control group.

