#### Retrospective review:

In addition to the 40 patients prospectively enrolled and randomized, a retrospective review will be performed on all patients undergoing major lower limb amputation from July 2017 through December 2020. These patients will be identified through an Epic report with inclusion/exclusion criteria the same as the prospective portion, with the exception of refusal to participate as this portion will have a waiver of informed consent.

Patients with a regional nerve block will be compared to those without on age, gender, race, BMI, ASA class, length of operation, hospital length of stay, and oral and parenteral narcotic pain requirements.

**Statistical Analysis:** The two groups will be compared using descriptive statistics. Continuous data will be analyzed using student's t-test and/or Mann-Whitney U tests and categorical data will be analyzed using Chi square analysis.

**Sample Size:** We expect to include approximately 1000 patients in this study.

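### Student's equal-variance t-test can be miscalibrated in the non-randomised cohort, where the block/no-block split is uncontrolled; Welch's test should be named instead

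*Combined protocol and SAP*

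**What the plan says.** The Statistical Analysis paragraph, placed under Retrospective review, gives the whole plan for continuous data: "Continuous data will be analyzed using student's t-test and/or Mann-Whitney U tests". It gives no rule for choosing between the two tests. It does not mention an unequal-variance version, a variance check, a transformation, a significance level or a confidence interval.

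The cohort comes from records: "a retrospective review will be performed on all patients undergoing major lower limb amputation from July 2017 through December 2020". Patients are grouped by whether they had a block, and the outcomes compared include "hospital length of stay, and oral and parenteral narcotic pain requirements". The Sample Size line reads: "We expect to include approximately 1000 patients in this study".

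A fixed split exists only in the randomised part of 40 patients, under Prospective enrollment: "Half of the patients were randomized into the treatment group, and half of the patients were randomized into the control group".

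**The concern.** Student's t-test, as the name is normally used, pools the two variances. Pooling is harmless in large samples when the groups are equal in size or equal in spread. The randomised part has the first safeguard by design. The cohort has neither: its split follows usual care, and nothing in the documents supports equal spread.

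If the smaller group is the less variable one, the pooled standard error is too large, and the test loses power. If the smaller group is the more variable one, the standard error is too small, and false differences are declared too often. Length of stay and narcotic requirement carry the study's hypothesis, and the cohort supplies most of the patients, so the calibration of this test matters.

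**Working it through.** **Inputs from the documents.** Total about 1000; randomised 40, split 1:1. If the 1000 includes the 40, the cohort is 1000 - 40 = 960. The figure of 1000 cannot be reproduced, because no alpha, power, effect, SD or split is given.

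**Assumed inputs.** Two-sided alpha 5%; block share p; SD ratio r (block divided by no block); lognormal outcomes in the simulations. None of these is in the documents, so ranges are shown.

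**Step 1: size of the pooled test at equal means.** Let k be the pooled standard error divided by the true one. In large samples

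k² = [p·r² + (1 - p)] / [(1 - p)·r² + p], and actual size = 2·[1 - Φ(1.96·k)].

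The sample size cancels, so a large cohort does not cure the problem.

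- p = 10%, r = 1.5: k² = 1.125/2.125 = 0.529, k = 0.728, size 15.4%.
- p = 10%, r = 0.67: k² = 0.945/0.504 = 1.875, k = 1.369, size 0.7%.
- p = 20%, r = 1.5: k² = 1.25/2.00 = 0.625, k = 0.791, size 12.1%.
- p = 20%, r = 0.67: k² = 0.890/0.559 = 1.591, k = 1.262, size 1.3%.

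| Block share | r = 0.67 | r = 0.8 | r = 1 | r = 1.25 | r = 1.5 |
|---|---|---|---|---|---|
| 10% | 0.7% | 1.9% | 5.0% | 10.1% | 15.4% |
| 20% | 1.3% | 2.5% | 5.0% | 8.6% | 12.1% |
| 30% | 2.2% | 3.2% | 5.0% | 7.3% | 9.3% |
| 50% | 5.0% | 5.0% | 5.0% | 5.0% | 5.0% |

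Simulation with lognormal data agrees. At N = 1000 and shares of 10-50%, the pooled test rejects 0.9-5.1% (r = 0.67) and 5.4-14.3% (r = 1.5). Welch rejects 4.9-5.2% and 5.4-6.9%. Runs at N = 960 put Welch at up to about 7.5% at a 10% share. In the randomised part (20 v 20, r = 1.5) the pooled test gives 5.0% and Welch 4.8%.

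**Step 2: what if spread only follows the mean?** Then equal means imply equal spread. Simulation with the same CV in both groups gives 4.4-5.6% for the pooled test at every share, so the null p-value is sound. Under a true difference the interval is still affected. For means of 6 v 8 days with equal CVs, r = 6/8 = 0.75, and coverage = 2·Φ(1.96·k) - 1:

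- 10% share: k² = 0.956/0.606 = 1.577, coverage 98.6%.
- 20% share: k² = 0.9125/0.65 = 1.404, coverage 98.0%.
- 80% share: k² = 0.65/0.9125 = 0.712, coverage 90.2%.
- 90% share: k² = 0.606/0.956 = 0.634, coverage 88.1%.

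Simulation puts the ranges at about 98-99% and 88-91%.

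**Step 3: power.** Means 6 v 8 days, CV 0.9, N = 960. A normal approximation gives Welch 91% v Student 80% at a 10% share. Simulation gives a smaller gap: 87% v 82%. At a 20% share it is 97.6% v 97.3%, and at 30% there is no gap (99.5% v 99.5%).

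**Step 4: limits of Welch.** With skewed data and a small group, Welch is mildly anti-conservative: about 6-7% at shares of 5-10% with equal CVs, and up to about 10% at a 5% share with CV 1.2 v 0.8. A studentised bootstrap with 48 block patients gave 7.1% in 800 runs, which is better but not fully corrected.

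**The case against.** The strongest reply is that the plan never commits to the pooled test. It offers Mann-Whitney as an alternative, which many analysts would choose for skewed stay and narcotic data, and it does not itself say that variances are pooled. This stands in part: the pooled test is a permitted analysis, not a settled one. Mann-Whitney is not a repair if the target is a difference in mean days or dose. With equal means and unequal spread it rejected 44-96% of the time in the simulations, because it does not test means. The plan, however, does not state that means are the target.

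A reader might infer that the cohort p-values are wrong because spread in stay and narcotic use rises with the mean. That does not follow. This mechanism leaves the null p-value intact (step 2); distortion needs spreads that differ at equal means, for instance through case mix, and the documents give no SDs. A reader might also infer that planned confidence intervals or error bars are faulty. None is planned, so the coverage figures apply only to intervals that might be reported.

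Nor is a small block group documented. The Background calls blocks part of usual care, and the Design section calls the injections standard of care, so the share could be moderate or high. Finally, the comparison is unadjusted, and Welch leaves its confounding untouched. All of this stands and limits the point.

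**Conclusion.** The point holds as a risk of miscalibration of unknown direction, confined to the non-randomised cohort. The only parametric test named is the equal-variance one, and the design does not control the split that would make it safe. With SD ratios of 0.67-1.5 at equal means, the size could be about 1-15% at a 10% share and 1-12% at 20%, against about 5-7.5% for Welch. If spread only tracks the mean, what remains is interval coverage under a true difference and some power when block patients are very few; the power gap is gone by a 20% share. Share, SD ratio, CV and mean stay are all assumptions. The point is modest, but the remedy is cheap and, as the retrospective review is described in the future tense, can still be adopted before analysis.

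**What to change.** In the Statistical Analysis paragraph, replace Student's t-test with Welch's unequal-variance t-test for the block v no-block comparison of length of stay and narcotic amount. Report the difference in means with its Welch 95% confidence interval. State in advance which test applies to each outcome, so that the choice is not left until the data are seen. If either group has about 100 patients or fewer, check the result with a studentised bootstrap interval, accepting that this improves coverage but may not fully restore it.

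The cost is one or two sentences and a software option, with no new data. The downside is Welch's mild anti-conservatism when a small group is strongly skewed. Confounding in the unadjusted comparison needs separate treatment.

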## **Regional Nerve Blocks for Major Lower Extremity Amputations: Effects on Postoperative Pain Control and Length of Stay**

**Synopsis:** This study will analyze patients undergoing major lower extremity amputations by the vascular surgery service at UCSF Fresno to determine if regional nerve blocks (sciatic and femoral) have any effect on postoperative pain control, narcotic requirements, and length of stay compared with standard post-operative narcotic regimens.

**Hypothesis:** We hypothesize that patients undergoing major lower extremity amputations with regional nerve blocks have better postoperative pain control, decreased narcotic requirements, and shorter length of stay when compared with patients who receive post-operative narcotic pain medications only.

**Specific Aims:** To determine if regional nerve blocks provide better postoperative pain control, decreased length of stay, and decreased narcotic requirements for patients undergoing major lower extremity amputations.

**Background and Significance:** Major lower extremity amputations (above knee amputation or below knee amputation) are common procedures performed for patients with end stage ischemia, infection, and/or disfigurement. Patients undergoing major lower extremity amputations have significant morbidity and mortality. Up to 95% of amputees report chronic pain, and inadequate pre- and postoperative pain control may increase the risk of chronic amputation pain. Additionally, there is a growing epidemic of narcotic overdoses in the United States. From 2000 to 2014, the age-adjusted drug overdose death rate has more than doubled from 6.2 per 100,000 persons to 14.7 per 100,000. The main drugs associated with overdose deaths are prescription pain medications.

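### Length of stay and narcotic use are compared as raw values with no handling of in-hospital death, so an early death can score as benefit in the non-randomised comparison

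*Combined protocol and SAP*

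**What the plan says.** The hypothesis, in the opening section, treats "decreased narcotic requirements, and shorter length of stay" as benefits of the block, along with better pain control. The Background in the same section states: "Patients undergoing major lower extremity amputations have significant morbidity and mortality". It gives no rate and does not say whether the deaths occur in hospital.

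Under Retrospective review, "a retrospective review will be performed on all patients undergoing major lower limb amputation from July 2017 through December 2020", with the trial's eligibility criteria apart from refusal to participate. Patients with and without a block are then compared on a list that includes "length of operation, hospital length of stay, and oral and parenteral narcotic pain requirements". The method for these variables is: "Continuous data will be analyzed using student's t-test and/or Mann-Whitney U tests". Chi-square is named for categorical data. The Sample Size line reads: "We expect to include approximately 1000 patients in this study".

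Under Prospective enrollment, "This study was a double-blinded randomized controlled trial analyzing 40 patients", and some patients are identified "following a consultation by the vascular surgery service in the hospital". That section also says that all trial patients have been discharged, without saying whether any left by death.

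No section defines the start or end of length of stay, gives a time base for narcotic use, lists in-hospital death as a data item, excludes patients who die, or says how their values are scored.

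**The concern.** Completeness of the data is not the issue. A patient who dies on day 3 has a correctly recorded stay of 3 days and has had little time to receive narcotics. Both planned tests read that record as a good result, because smaller values are what the hypothesis predicts. If deaths differ in frequency or timing between block and no-block patients, part of the observed difference in stay reflects mortality rather than recovery.

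The retrospective comparison is not randomised, so such a difference is plausible. The Background itself describes blocks chosen for four ASA class 4 patients with severe cardiac insufficiency. If sicker patients tend to receive blocks, early deaths would flatter the block; if the imbalance runs the other way, they would hide a benefit.

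A related gap is where the count starts. If stay runs from admission, patients found by inpatient consultation carry preoperative days that a block given at surgery cannot change.

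**Working it through.** **The plan's own figure.** The expected total of about 1000 patients is a count, not the result of a power calculation. No alpha, power, effect or SD is given, so there is nothing to reproduce.

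**Inputs.** From the documents: about 1000 patients in total, 40 of them randomised half and half. Assumed, because the documents are silent:
- 1000 − 40 = 960 retrospective patients, 30% with a block, so 288 v 672
- survivor stay lognormal, median 8 days, log-SD 0.7
- no true effect of the block
- early deaths have a median stay of 4 days with the same log-SD
- two-sided 5% tests

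**Mean shift.**
- Mean survivor stay = 8 × exp(0.7²/2) = 10.22 days
- Mean stay of early deaths = 4 × exp(0.7²/2) = 5.11 days
- Shift between groups = difference in mortality × (5.11 − 10.22)

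| Mortality | Shift in the higher-mortality group |
|---|---|
| 5% v 3% | 0.02 × (−5.11) = −0.10 day |
| 10% v 5% | 0.05 × (−5.11) = −0.26 day |
| 15% v 5% | 0.10 × (−5.11) = −0.51 day |

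**False differences, t-test (normal approximation).** SD = 10.22 × √(exp(0.49) − 1) = 8.13. SE = 8.13 × √(1/288 + 1/672) = 0.57 day.
- 10% v 5%: 0.26/0.57 = 0.45 SE, rejection about 7%
- 15% v 5%: 0.51/0.57 = 0.89 SE, rejection about 14%
- 5% v 3%: 0.10/0.57 = 0.18 SE, rejection about 5%

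Simulation of the same settings agrees: about 7-10% across the two tests at 10% v 5%, and about 15% (t-test) and 24% (Mann-Whitney) at 15% v 5%. At 5% v 3% rejection was 5-6%.

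**Other inputs.** With 500 v 500 patients, survivor median 7 days and the stays of patients who die cut to 40%:
- 10% v 5%: 0.25 day, rejection 9% (t-test) and 13% (Mann-Whitney)
- 15% v 5%: 0.54 day, rejection 23% and 41%
- equal mortality of 5%: rejection near 5%

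**Timing of deaths, 288 v 672.** If patients who die stay as long as survivors, the shift is zero and rejection is about 5%. If they stay 1.5 times as long, their mean is 1.5 × 10.22 = 15.33 days, and 15% v 5% gives 0.10 × (15.33 − 10.22) = +0.51 day, the opposite sign.

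**The trial.** At 20 per arm, one death on day 2 where 10 days is typical moves that arm's mean by (10 − 2)/20 = 0.4 day. In simulation with 20 per arm, rejection stayed at 3-6% in every scenario.

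**Worst-rank scoring.** Giving deaths the worst rank in the Mann-Whitney test, with no effect in survivors (288 v 672), led to rejection about 24% of the time at 10% v 5% and 69% at 15% v 5%, against the group with more deaths.

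**Narcotics.** No size can be given, because the documents state neither the measure nor its time base.

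**The case against.** A reader might infer that every death counts as a short stay, or that the plan is biased towards the block. The documents support neither. They say nothing about when deaths occur, and the sign of the shift depends on that. They give no mortality rate. Emergency and staged amputations are excluded, which may lower mortality. At 5% v 3% the distortion is negligible.

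A second objection is that the scenario isolates death too neatly. A group with higher mortality may also have sicker survivors who stay longer. If its survivors stay 5% longer, its mean at 10% mortality is 0.90 × 1.05 × 10.22 + 0.10 × 5.11 = 10.17 days. The other group, at 5%, has 0.95 × 10.22 + 0.05 × 5.11 = 9.96 days, so the sign changes. Confounding is then the larger problem, and no rule for death repairs it.

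Third, narcotic use might be recorded per day, which would be less affected. The documents nowhere say that it is totalled. Nor do they say that stay is counted from admission.

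All of this stands as a limit on direction and size. It does not supply the missing rule. A direction that depends on unknown timing is itself a reason to fix the handling of deaths before the data are analysed.

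**Conclusion.** The point holds in conditional form. As written, the plan scores an early in-hospital death as a favourable stay and, if narcotics are totalled, as favourable narcotic use, in a population that it describes as having significant mortality.

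The concern lies mainly in the retrospective comparison and requires deaths to differ between groups in frequency or timing. Under the assumed inputs the distortion runs from about 0.1 day (5% v 3%) to about 0.5 day (15% v 5%) when deaths come early. The false-difference rate then reaches about 15% to 24%, depending on which of the two named tests is used. With survivor-like stays it is nil, and with longer stays it reverses.

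A reader might also infer that the randomised result is compromised. The documents do not support that: the effect at 20 per arm is small, and they report no in-hospital death in the trial, although discharge by death is not ruled out. The change should be made, and since the retrospective review is described as still to be performed, it can be prespecified.

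**What to change.** - Add surgery date and discharge status (alive or dead) to the Epic extract.
- Define stay as days from surgery to live discharge. This also removes preoperative days for patients found by inpatient consultation.
- Compare the cumulative incidence of live discharge between groups, with in-hospital death as a competing event.
- Express narcotic use per day alive in hospital within a fixed early postoperative window, stated in advance.
- Report in-hospital deaths by group beside these results.

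Worst-rank scoring of deaths should be at most a sensitivity analysis. It turns the comparison into a composite of stay and death and carries confounded mortality into it, as the 24% and 69% rejection rates show.

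The cost is a few sentences of analysis text, two extract fields, a less familiar summary of stay and slightly more analysis. The change does not remove confounding between block and no-block patients, which needs its own adjustment.

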#### **Confidentiality and Privacy:**

Prospective subjects are assigned a unique ID with the key stored separate from the data collected. All completed informed consent forms are stored in a locked file cabinet

Protocol Version Date: 01/11/2021

Page 4 of 5

located within the locked Trauma Program office in Community Regional Medical Center.

Retrospective subjects will be identified by an Epic report created by the study coordinator. Subjects will not be contacted for this study and will be included with a waiver of informed consent. These subjects will also be identified by a unique ID with a key stored in a password-protected spreadsheet accessible to members of the study team.

Study documents will be stored for at least six years or until after the study is completed, whichever is longer. At that time, all electronic documents will be destroyed per CMC policy and paper documents will be discarded in the confidential shredding bins in the Department of Surgery at CRMC.

**Data Security:** The data is kept on the hospital server that has limited rights access.

